**C9. COVID-19 and Intervention Locations. Group intervention will not occur in Phase**

**Orange. They will only commence if we are moved to Phase Yellow.** The Yoga + MR intervention is scheduled to be held in the back of the VASD chapel area on Wednesdays afternoons from 2-3:30PM. When chairs are cleared, this area is approximately 40 ft x 50ft or 2000 square feet area. This has been approved by Chaplain [name]. This large area allows for social distancing of 10 feet or greater between participants. With two cohorts, 8 participants are randomized to each intervention at a time. Attendance is expected to be 6-8 subjects each session. The Relaxation class intervention will also be held in the same space. Subjects at normal risk will be allowed to attend following RAMP up guidelines, including social distancing, the use of PPE, COVID-19 consent addendum, and COVID-19 symptom screening.

**C10. Measures.** Measures will include questionnaires and two physiological measures. Questionnaires are described in section 9.8 To reduce in-person contact during the COVID-19 pandemic, we will allow participants to complete follow-up assessments by mail if they cannot be scheduled for an in-person assessment, or if their status changes from normal risk to higher risk, or if they become infected. If this occurs, we will forego the physiological assessments below.

Physiological measures include grip strength and a one-leg balance test.

**Grip Strength.** Grip strength in both hands of each participant will be measured using an adjustable, hydraulic grip strength dynamometer (Jamar Hydraulic Hand Dynamometer, Model No. BK-7498, Fred Sammons, Inc. Burr Ridge, IL). Two trials will be conducted for each hand. In cases of current pain flare-ups or recent procedures to a hand or wrist, the affected area is not tested, and the result of the one good hand is used. The best performance of two trials will be selected for each side, and the average of the left and right hand will be used for analysis. Reproducibility for grip strength assessment has been shown to be high:  $r=0.88-0.92$ . Predictive validity of hand grip strength has been shown previously for both disability and mortality.

**One-leg Stance** - Balance was evaluated using the unipedal stance test, aka the single leg stance. Which is a frequent measure of fall-risk in older adults, but is also frequently used in back pain research. It has been validated and has referenced norms across all adult age groups. The test was administered by research staff with calibrated stopwatches. The participant was instructed to alternately stand on one leg for as long as they could with both eyes open for a maximum of 60 seconds. They were then instructed to repeat the test with both eyes closed.

**C11. Data Analytic Methods.** Because our aims focus on acceptability, feasibility, fidelity and AEs in preparation for a larger RCT, tests of statistical significance are not required. Intervention acceptability and the feasibility of conducting a full-scale RCT will be evaluated using recruitment rates, recruitment to enrollment ratio, intervention attendance rates, retention rates at 12-week assessment, participant satisfaction, serious and non-serious AE rates, participant assessment burden, and instructor fidelity. Mean differences from baseline to follow-up scores will be calculated for outcome measures.

**C11.1. Data management.** Questionnaires will be formatted by the project coordinator to reduce recording errors and facilitate computer scanning and verification. The project coordinator will monitor the quality of the questionnaire data as soon as they are collected to achieve prompt resolution of errors and omissions. Forms will be coded to protect confidentiality. Coded forms will be transported by study staff to the University of California Health Services Research Center (UCSD-HSRC) for processing. UCSD-HSRC is a recharge unit within UCSD that provides research services to outside entities. They are located at [name]. An approved Authorization to Transport (ATT) form will be used and on file for staff transporting the paper copies. All identifiers will be removed from the form except a subject ID code. Data will include sociodemographic data, coded interview transcripts, and health outcome data, but will not contain age, birthdate, or any of the 18 patient identifiers. The key to the coded data is kept on the PI's private folder on the VA research network on the VA server. In addition, the key linking names to ID numbers will be stored in a locked file cabinet within a locked research office in Bldg. 13 of VASDHS. UCSD-HSRC will scan and conduct quality review of data. They will manage clean data and prepare a data set for analysis. The data file will be password protected and transported back to VA by study staff or sent by MS Azure if under 40Mb.

Audio recordings of qualitative interviews will be transcribed by a VA service. The service is VA Salt Lake Centralized Transcription Services Program, a program that was created to provide VA researchers nationwide with transcription and qualitative analysis services. Identifiable voice data will not leave the VA secure IT environment. It will be transferred via a secure VA Sharepoint folder. Transcripts with study ID codes will be returned to PI-[name] via VA Sharepoint. The

Centralized Transcription Services Program will not use the data for any other purposes and is only providing transcription as a paid service.

**C11.2. Data Analysis and Feasibility Criteria.** Recruitment rates will be compared to the specified goal of a mean of 4 enrolled participants per month. We expect to need 5 screened eligible participants per month because some fail to follow through and enroll. If rates remain below 50% of the goal, feasibility will not be established for a full-scale RCT. Attendance rates in many mind-body intervention studies range between 50-80%. For this study, attendance of 50% or higher will be required to support further research on either intervention. A retention rate of 80% or higher is considered an adequate retention rate at a post-intervention assessment for an RCT. Thus, we will use a slightly more lenient 75% or higher retention to indicate feasibility to proceed. Participant satisfaction rates of 75% or higher (measured as % of participants checking agree or strongly agree) will be used to indicate acceptability of the interventions, with little or no modifications needed prior to a larger study. AEs will be evaluated in collaboration with the VASD IRB and the DSMC. In general, any more than 1-2 serious AEs attributed to either intervention among the 20 participants assigned to each would give cause for pausing the intervention until obvious solutions and modifications were identified. Mean time to complete the questionnaires is estimated at 40 minutes. Mean time of 80 minutes or more would indicate burden issues and review of the battery and/or compensation level. Instructor fidelity of under 75% will indicate a need for retraining and/or clarifications of the instructor manual. Finally, mean changes on outcome measures will be compared to minimum clinically important differences where established.

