C1.1. Aim 1 & 2: The interventions will be adapted in four main ways; a) to safely benefit cNP patients; [b) to ensure it is trauma-sensitive; c) includes additional emphasis on relaxation and stress reduction; and d) to include shorter MRP training sessions. Aims 1 and 2 will leverage ongoing work from the PI's current NCCIH-funded R34 in which the yoga for clBP intervention is being adapted to benefit cNP patients. To ensure trauma-sensitivity, study investigators will build on an intervention designed by co-inv. [name] and other study RR&D-funded protocols (Drs. [name] and [name]) to align the intervention with principles outlined by Emerson et al. The additional relaxation and stress reduction emphasis is designed to alleviate PTSD symptoms in addition to chronic pain.] The MRP will be shortened to an initial 30-minute training followed by 15-minute brief interventions sessions and home practice assignments by [name] who has done preliminary work on adapting MRP for briefer sessions and delivery by phone or Internet. Study investigators will review literature, other protocols, and the revised MRP prior to participating in a half-day intervention refinement conference at VASD. Further intervention refinement will occur at project meetings and a manual will be produced.

C1.2. Aim 3: [we will recruit and randomize 32 VA patients formally diagnosed with PTSD and chronic clBP and/or cNP to enhanced yoga or the R/HE control. We plan to recruit starting in month 4, and will begin randomizing when we reach enrollment of 16, which is expected by month 6-7. The first set of interventions will start in month 8 and run for 12 weeks. We will repeat this process with ongoing recruitment of another 16 participants between months 8-12, with interventions running months 13-16. Participants will complete physiological and self-reported outcomes assessments at baseline, 12 weeks, and 18 weeks after enrollment. Assessments will take about 40 minutes each and participants will be compensated \$40 for each completed assessment. We will also conduct qualitative interviews with 7-8 yoga participants and 4-5 R/HE comparison participants to obtain in-depth feedback on satisfaction and areas that could be improved before a larger trial is conducted.] If feasibility, acceptability, and safety are established, the primary health outcome of interest for a subsequent trial is pain-related disability/ functioning (Roland Morris Disability Questionnaire (RMDQ)).

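### For participants whose tested hands differ between visits, the grip-strength change score subtracts two different quantities

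*Combined protocol and SAP*

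**What the plan says.** The scoring rule is in Section 9, C10 Measures, under Grip Strength. Each hand gets two trials, and its better result is kept. By default, "the average of the left and right hand will be used for analysis". There is one exception. "In cases of current pain flare-ups or recent procedures to a hand or wrist", the plan says that "the affected area is not tested, and the result of the one good hand is used".

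The timing is in C1.2: "Participants will complete physiological and self-reported outcomes assessments at baseline, 12 weeks, and 18 weeks after enrollment". The analysis is in C11: "Mean differences from baseline to follow-up scores will be calculated for outcome measures". C11.2 adds that "mean changes on outcome measures will be compared to minimum clinically important differences where established".

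No section requires the same hand or hands to be scored at the visits being compared, restricts change to hands tested twice, or asks for a record of which hand was scored. The only other provision on missing physiological data is in C10: these tests are skipped when a follow-up is completed by mail.

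**The concern.** One variable has two definitions, and hand status on the day of testing decides which applies. A flare-up can start or settle, and a procedure can stop being recent, between baseline, 12 weeks and 18 weeks. The same participant can then be scored on two hands at one visit and on one hand at another.

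As a score for a single visit, the exception is reasonable. The difficulty arises on subtraction. If the two hands differ in strength, part of the change comes from which hands were in the score and not from any gain or loss of strength. The mean change in grip would carry that component, with no flag in the data to show it. C1 says that a similar design will be proposed for the full-scale trial, so the rule could be carried forward.

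**Working it through.** The plan states no figure on this point, so there is none to reproduce. The check is algebra on the stated rule, followed by a range on assumed values.

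**Algebra.** Let R and L be the best values for the right and left hand, with no true change between visits. Suppose that the left hand is the one left untested.

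- Both hands at baseline, right only at follow-up: R - (R + L)/2 = (R - L)/2.
- Right only at baseline, both hands at follow-up: (R + L)/2 - R = -(R - L)/2.
- Right only at baseline, left only at follow-up: L - R.
- Same hand or hands at both visits: 0.

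The error does not depend on there being no true change. With subscripts for visit, (R2 + L2)/2 - R1 = (R2 - R1) - (R2 - L2)/2. This is the same-hand change minus half the gap between the hands at the visit where both were tested.

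**Sign.** If the untested hand is the weaker one, its return at follow-up shows as a fall, and its loss at follow-up shows as a rise. If the untested hand is the stronger one, both signs reverse.

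**Inputs for size.** From the documents: 32 participants, with 8 randomized to each intervention in each of two cohorts (Section 9, C9), so n = 16 per arm; and a retention threshold of 75% (C11.2), so 0.75 × 16 = 12 per arm. Assumed, because the documents do not give them: a two-hand mean M of 30 to 40 kg and a between-hand difference D of 5, 10 or 20% of M.

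**Error per affected participant.** The size is D/2 when moving between two hands and one, and D when the tested hand switches. The arm-mean shift with k participants erring in the same direction by D/2 is k × (D/2)/n.

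| D as % of M | D/2, kg | D, kg | Shift, k = 2, n = 16, kg | Shift, k = 2, n = 12, kg |
|---|---|---|---|---|
| 5 | 0.75 to 1.0 | 1.5 to 2.0 | 0.09 to 0.13 | 0.13 to 0.17 |
| 10 | 1.5 to 2.0 | 3.0 to 4.0 | 0.19 to 0.25 | 0.25 to 0.33 |
| 20 | 3.0 to 4.0 | 6.0 to 8.0 | 0.38 to 0.50 | 0.50 to 0.67 |

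For example, the top of the range is 40 × 0.20/2 = 4.0 kg per participant, and 2 × 4.0/16 = 0.50 kg in the arm mean. With D = 0 every entry is zero.

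**How often.** The documents give no frequency. If a one-hand test has probability q at any visit, independently between visits, a participant moves between one hand and two across two given visits with probability 2q(1 - q). The chance of at least one among 32 is 1 - (1 - 2q(1 - q))^32.

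| q (assumed) | 2q(1 - q) | Expected of 32 | Chance of at least one |
|---|---|---|---|
| 2% | 0.039 | 1.3 | 0.72 |
| 5% | 0.095 | 3.0 | 0.96 |
| 10% | 0.180 | 5.8 | above 0.99 |

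**Comparison with retest noise.** C10 gives a reproducibility of r = 0.88 to 0.92. With an assumed between-person SD of 8 to 10 kg, the retest SD of a change is SD × √(2(1 - r)): from 8 × √0.16 = 3.2 kg to 10 × √0.24 = 4.9 kg. Over 16 participants that is 3.2/4 = 0.8 to 4.9/4 = 1.2 kg in the mean.

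**The case against.** The strongest reply is that this is a small gap in a secondary measure of a feasibility pilot. C11 says that "tests of statistical significance are not required", the thresholds in C11.2 do not involve grip, and C1.2 names the Roland Morris questionnaire as the health outcome of interest for a later trial. The comparison with clinically important differences applies only where these are established, and the documents state none for grip. The default is both hands at every visit, so most participants may be unaffected. Choosing the best trial for each side means that per-hand values exist at scoring, so the matter can be settled at analysis. On the assumed values, the arm-mean shift with two affected participants is also smaller than ordinary retest noise. All of this stands, and it limits the importance of the point. It does not make the subtraction valid, because the stated rule, followed literally, gives a wrong change score for those it affects.

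Two stronger readings are tempting, and the documents do not support them.

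- A reader might infer that the error has a fixed direction and counts against an arm that relieves pain, because a weak, painful hand that recovers pulls the average down. The sign depends on which hand is untested and at which visit. The trigger is a hand or wrist problem, whereas participants are enrolled for back or neck pain. Nothing says that either arm is expected to change hand or wrist status, and the rule is the same in both arms.
- A reader might take a larger shift from a wide gap between the hands. With 41 and 30 kg at follow-up and 40 kg on the right hand alone at baseline, the rule gives 35.5 - 40 = -4.5 kg against a same-hand gain of 1 kg. Two such cases would move the mean of 16 by 2 × 5.5/16 = 0.69 kg. That gap is 11/35.5 = 31% of the mean, beyond the 5 to 20% range used here, and nothing in the documents supports it.

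**Conclusion.** The point holds, within limits. For participants whose tested hands differ between the visits compared, the plan's rule yields a change score with a spurious component of half the between-hand difference, or the whole difference if the tested hand switches. This goes beyond missing detail, since both the scoring rule and the subtraction are stated.

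The size rests on assumptions throughout: about 0.75 to 4 kg per participant who moves between two hands and one, and about 0.1 to 0.5 kg in the arm mean when two of 16 err in the same direction. If errors run in opposite directions they partly cancel. With fewer grip measurements, for instance after mailed follow-ups, each affected participant weighs more. What is shown is avoidable error of either sign in one of two physiological measures, not a bias against either arm, and no go/no-go decision depends on it. It is a minor correction.

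**What to change.** Add an analysis rule to C10 or C11:

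- Keep the best value for each hand at each visit, and record which hands were tested.
- Compute change only from the hand or hands tested at both visits being compared: the average where both hands were tested twice, otherwise the single hand in common.
- Set the change to missing where no hand is common to the two visits.
- Report, by arm and visit, how many change scores rest on one hand and how many are missing for this reason.

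The spurious component is then exactly zero. The cost is a few sentences and no new measurement, since C10 already obtains a value for each side. The downside is that a few change scores will rest on one hand or be missing. The decision not to test an affected hand is unchanged.

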## Section 9.1 Clinical Procedures

### 9.1) Differentiate research procedures (or any procedures done for research purposes only) from clinical procedures (procedures that are done as part of standard care).

(Note: this differentiation should be clear in the consent form as well)

All of the procedures will be considered research procedures. Mantram Repetition classes are offered at VASD as a clinical intervention, but when shortened and combined with yoga for this intervention, it will be considered research.

## Section 9.8 Questionnaires & Surveys

### 9.8) Provide the name and a reference for questionnaires/surveys that are standard or identify them here and attach a copy of the questionnaire/survey. *Questionnaires or surveys that are not clinical standard references must be uploaded. Reference the help link for additional information related to surveys administered to VA personnel and approved platforms for web-based surveys.*

C9. Measures. Medical records will provide information on co-morbid diagnoses, medication usage, and ongoing treatments for screening and to further describe participant characteristics.

C9.1. Feasibility of recruitment and retention. We will track and document the date that each recruitment method begins and the date each person is recruited. We will ask each potential participant to identify the recruitment source that led to their inquiry about participation. We will track retention rates, reasons for not completing the follow-up assessment and acceptability of the assessment procedures.

C9.2. Acceptability, Attendance, and Adherence will be assessed using sign-in logs verified by the instructor. Self-reported practice of yoga and MR will be assessed with weekly logs. The yoga log is shown in Appendix 7 and a draft of the MR log is shown in Appendix 8. Participants will be called to document reasons for non-attendance. We will assess program satisfaction using questions developed and used by the investigators in previous studies. (Appendix 9). We will also conduct qualitative interviews with 7-8 participants of the enhanced yoga group and 4-5 participants of the R/HE comparison group to obtain in-depth feedback on satisfaction and areas that could be improved before a larger trial is conducted. Semi-structured qualitative interviews lasting ~ 45 minutes will utilize open-ended questions to address: 1) past experience with mind-body interventions; 2) their experience with the enhanced yoga program; 3) recommendations for changes; 4) feedback on dosing and logistics of the program; and 5) thoughts on research participation and assessment burden. Transcribed interviews will be analyzed using directed content analysis (DCA) to identify and categorize meaningful and detailed information about participant's opinions, perceptions and experiences. Verification of emergent themes and

disagreements during theme interpretation or coding hierarchy will be resolved through investigator discussions before completing the qualitative analysis.

**C9.3. Adverse Events:** AE information will be collected via a weekly log. (Appendix 10) Participants are instructed to contact intervention instructors or study staff if they experience any health problems possibly related to the interventions. AEs will be assessed by phone if intervention sessions are missed. Medical records will be reviewed if patients cannot be contacted to complete assessments or assess absences. We will establish a Data Safety Monitoring Committee (DSMC) at start-up.

**C9.4. Treatment Fidelity:** Instructor fidelity to the enhanced yoga interventions will be evaluated by review of video recordings of intervention sessions. Intervention instructors will be video-recorded. Instructors and participants will be aware of and consent to the recordings. Of the 12 videotaped sessions, one session from weeks 1-4, weeks 5-8, and weeks 9-12 will be randomly selected for review by an expert yoga instructor. They will review the sessions using a manual checklist for instructor adherence to the yoga manuals.

**C9.5. Health Outcomes.** Outcomes measures anticipated for use in a full-scale study will be administered to gauge participant burden and observe changes. We will assess basic socio-demographics along with military rank and duties, type/date of trauma, and combat status.

**C9.5.1 Pain-related Function.** The RMDQ has 23 questions asking about limitations experienced with daily activities. The scale is reliable and well validated. It has been used in other yoga studies. Questions will be worded to include limitations related to chronic back or neck pain.

**C9.5.1a. Neck Disability Index** - A validated index with 10 questions about neck pain-related functioning.

**C9.5.2 Pain severity and interference** will be measured with the Brief Pain Inventory (BPI).

**C9.5.3 PCL-5.** The PCL-5 is a 20-item self-report measure assessing 20 DSM-5 symptoms of PTSD. 

**C9.5.4 Traumatic Brain Injury.** Presence and severity of TBI will be assessed and classified as either mild or moderate/severe, using four screening questions. Mild TBI is defined as: Loss/alteration of consciousness < 30 minutes, Glasgow coma scale of 13-15 (if known), and post-traumatic amnesia of < 24 hours.

**C9.5.4a** The PHQ-9 contains 9 questions about depression and mental health. It is a validated measure.

**C9.5.5 The Insomnia Severity Index (ISI)** is a 7-item instrument that assesses the impact of insomnia.

**C9.5.6 Health-related Quality of Life** will be measured with the SF-12, a descriptive measure with two domains of HRQOL. Reliability and validity are well established. The EQ5D will also be used as a validated measure of preference-based quality of life.

**C9.5.7 Alcohol Use.** AUDIT-C is a 3-item screen for problem drinking and will refer to alcohol use over the past 3-month period. The measure has questions on typical consumption and binge drinking frequency.

**C9.5.8 Non-VA Medications/Treatments.** We will assess medications and self-care treatments used outside of VA via a questionnaire used in other VA studies. (Appendix 11)

**C9.5.9 The Philadelphia Mindfulness Index** has 20 questions that ask about awareness of the present moment, and acceptance of current situations. It is a validated measure.

**C9.5.10 The Fatigue Severity Scale** is a validated measure of fatigue symptoms. It has 9 questions.

**C9.5.11 The Self-Efficacy for cLBP scale** is a validated scale with 6 questions about one's confidence in their ability to manage their cLBP.

**C9.5.12 Program Evaluation** - Here we ask 10 questions about participant satisfaction with the interventions.

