## Section 9.9 Data Safety Monitoring Board or Plan

## 9.9) Provide a Data Safety Monitoring Plan (DSMP) or the details of a Data Safety Monitoring Board; if a written plan is available, attach a copy of the plan to the submission form.

The study is a pilot intervention that will randomize 32 participants with PTSD to either yoga plus Mantram repetition or to a relaxation comparison group. Study investigators will review all adverse events on a weekly basis and report them as appropriate to the IRB according to established requirements. Drs.[name] and [name] have clinical and research expertise with PTSD. If the rate of serious adverse events attributed to either intervention results in an imbalanced SEA rate between the two study arms, or is higher than clinically expected, the study will be stopped to assess safety. If adjustments to the intervention to remedy the problem are not obvious or easily made, the study intervention(s) will be discontinued.

Research activities will cease if any participant or study staff member that had recent study interactions with study staff or other participants tests positive for COVID-19 within 3 weeks of those interactions. All at risk persons will be notified of their risk at that time.

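### Adverse events are not ascertained the same way for every participant, and collection after the last session is left unspecified

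*Combined protocol and SAP*

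**What the plan says.** Section 9.8, C9.3 gives four routes by which an adverse event can reach the study:

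- "AE information will be collected via a weekly log". No first or last week is given. The log itself (Appendix 10) is not in the text supplied.
- "Participants are instructed to contact intervention instructors or study staff if they experience any health problems possibly related to the interventions". No time limit is given.
- "AEs will be assessed by phone if intervention sessions are missed". Only an absence prompts this call.
- The fourth route is a chart search, which depends on failed contact: "Medical records will be reviewed if patients cannot be contacted to complete assessments or assess absences".

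The opening of the measures text in Section 9.8 gives records a different role: "Medical records will provide information on co-morbid diagnoses, medication usage, and ongoing treatments for screening and to further describe participant characteristics".

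On timing, C5 and C8 in Section 9 give 12 weekly sessions in each arm, and C1.2 says: "Participants will complete physiological and self-reported outcomes assessments at baseline, 12 weeks, and 18 weeks after enrollment". C10 allows follow-up assessments by mail in some circumstances. Section 9.9 has the investigators review AEs every week, with no end date.

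On use, C11 counts "serious and non-serious AE rates" among the feasibility measures. C11.2 pauses an intervention when more than 1-2 serious events are attributed to it. Section 9.9 stops the study for a safety assessment if attributed serious events produce an "imbalanced SEA rate between the two study arms" or run above clinical expectation.

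**The concern.** The four routes do not apply equally to all participants. The phone call needs a missed session. The record search needs a failed contact. A participant's own report needs that person to suspect a link with the intervention, so relatedness is filtered by the participant before any investigator can judge attribution. Someone who attends, can be reached and does not suspect a link is covered by the log alone, for as long as the log runs.

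After the last session the missed-session call has no trigger, while exposure may continue: yoga participants hold a home-practice manual (C5) and are encouraged to use mantram repetition in daily life (C6). If the log also stops then, a reachable participant's event is recorded only if that person raises it.

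At stake are a stated feasibility outcome and two safety rules that work on very small counts. A favorable safety reading would be hard to interpret if it is unclear who was asked what, and until when.

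**Working it through.** **1. Each route, side by side (Section 9.8, C9.3)**

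| Route | Who is covered | After the last session |
|---|---|---|
| Weekly log | Everyone, as written | Not stated |
| Participant's own report | Anyone who suspects a link | Continues, passive |
| AE phone call | Those who miss a session | No trigger |
| Record review | Those who cannot be contacted about an absence or an assessment | Applies on failed contact for an assessment, including week 18 |

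**2. What the 12- and 18-week assessments contain.** The questionnaires in Section 9.8 (C9.5.1 to C9.5.12) cover pain and function, PTSD, TBI, depression, insomnia, quality of life, alcohol, non-VA treatments, mindfulness, fatigue, self-efficacy and satisfaction. The physiological measures in Section 9, C10 are grip strength and one-leg stance. None is an AE enquiry. A mailed assessment may also remove the conversation in which an event might surface. Section 15 prompts for the frequency of safety data collection, but the answer there gives neither a frequency nor a window.

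**3. How many would have no record review through a missed assessment.** Inputs: 32 participants (Section 2a; C1.2) and the 75% retention threshold (C11.2), which C11 applies to the 12-week assessment. Retained: 32 x 0.75 = 24. Not retained: 32 - 24 = 8, or 4 of 16 per arm if equal. The 8 is a ceiling, because only those who also cannot be contacted trigger a search. At least 24 of 32 would therefore have none by this route. At an assumed retention of 80% the figure is 25.6 (about 26), and at 90% it is 28.8 (about 29).

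**4. How sensitive the pause rule is to missed events (illustration only).** The documents give no event risk and no capture fraction, so both are assumed. Take 16 per arm (two cohorts of 8, Section 9, C9), a true risk p of an attributed serious event, and a fraction c that is captured. With q = p x c, the chance of recording 3 or more is 1 minus the sum over k = 0, 1, 2 of C(16,k) q^k (1-q)^(16-k). For p = 0.10 and c = 1 this is 1 - (0.1853 + 0.3294 + 0.2745) = 0.211.

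| True risk | Full capture | Two-thirds | Half |
|---|---|---|---|
| 10% | 0.211 | 0.086 | 0.043 |
| 20% | 0.648 | 0.362 | 0.211 |

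Reading the rule as 2 or more, the 10% row becomes 0.485, 0.289 and 0.189. C11.2 itself speaks of 20 per arm, which does not match 32 randomized; with 20, the 10% row for 3 or more is 0.323, 0.145 and 0.075. The pattern is the same in each case. These figures show only that a rule set at such low counts responds strongly to capture; they do not estimate capture in this trial.

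**The case against.** The plan can fairly be defended as a layered scheme with the same procedures in both arms, backed by weekly investigator review, the IRB and a monitoring committee, in a pilot that plans no significance tests. Record review then stands in for people whose own report has been lost. Much of this stands, and it rules out several stronger readings.

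- *A reader might infer that events after week 12 are not sought at all.* Failed contact for the week-18 assessment triggers record review, participants' reports have no time limit, and the log has no stated end.
- *A reader might infer that 6 of the 18 weeks have no active collection.* That requires the log to stop with the sessions and week 0 to be the start of the intervention. The text does not state the first. On the second, C1.2 times assessments from enrollment, with recruitment from month 4 and interventions from month 8.
- *A reader might infer that a regular attender's hospital stay comes to light only if volunteered.* During the sessions the log operates, and a stay that causes a missed session prompts a call.
- *A reader might infer that the arm with more drop-out gets the more sensitive search.* No text shows that a VA record search finds more than log, call and self-report together. C9.5.8 expects some care outside VA, which a VA search could miss, so the direction is open.

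The defense does not supply a closing date for AE collection, a standard enquiry at follow-up, or a record search that applies to everyone.

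**Conclusion.** The point holds in a limited form. Ascertainment in C9.3 depends on attendance, contact and the participant's own view of relatedness. For reachable participants, collection after the last session is unspecified and, unless the log continues, passive. AE rates and the attributed serious-event counts behind the pause and stop rules may therefore be too low. They could also differ between arms for reasons unrelated to safety, but only if absence or non-contact differs by arm, on which the documents are silent.

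Neither the size nor the direction of any distortion can be stated from the documents. The conclusion rests on the text supplied; Appendix 10 might settle the log's content and duration, but it would not make record review uniform. This is a worthwhile, inexpensive improvement, not a flaw that makes the safety data uninterpretable.

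**What to change.** In Section 9.8, C9.3:

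1. State that AE collection runs from randomization to the 18-week assessment, and say whether the weekly log continues after the last session.
2. Ask all participants in both arms the same AE and serious-AE questions at 12 and 18 weeks, including in mailed packets, for all health problems whether or not they are thought related. Attribution then rests with the investigators.
3. Apply the same VA record search for hospitalizations and emergency visits to all 32 participants over that window, whatever their attendance or contact status.
4. In C11, report AE rates by arm for that window.

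The cost is a few more minutes at two existing assessments, a brief chart search for 32 consented participants whose records the study already opens (Sections 11 and 27), and more unrelated events to classify.
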